14.3 Statistical Analysis Endpoints

14.3.1 Primary Endpoint

Incidence of hernia recurrence within 12 months will be calculated on the FAS subjects who reach the 12-month follow-up including any subject with hernia recurrence diagnosed within the 12-month period following surgery (even if the subject has withdrawn from the study before the 12-month assessment).

The primary endpoint will be summarized using count, percentage, and the corresponding 95% confidence interval. Sub-group analyses on primary endpoints will be performed according to study needs and will be described in the Statistical Analysis Plan and the Clinical Study Report.

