14.3.2 Secondary Endpoints

- Incidence of ADEs intra-operatively will be calculated on the FAS subjects who reach the corresponding time point, including any subject experiencing hernia recurrence, AEs or ADE within the corresponding follow-upperiod.
- Incidence of hernia recurrences will be calculated on the FAS subjects who reach the corresponding time point.
- Time to hernia recurrence, as well as time to AE occurrence analyses will be run using Kaplan Meier estimate and curve.
- Subject quality of life (QoL) questionnaires will be evaluated using the Carolinas Comfort
 Scale™ (Appendix B), and statistical analysis will follow the corresponding analysis guideline.
- Length of hospital stay will be summarized using count, mean, standard deviation, median, minimum, and maximum.

Subgroup analyses on secondary endpoints will be performed according to study needs and will be described in the statistical analysis plan and the clinical study report.

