14.5 Sample Size Determination

Sample size has been determined based on an acceptable level of accuracy for the estimated rate of hernia recurrence at 12 months (primary endpoint).

Previous studies of the predicate device (Proceed™ Surgical mesh) with similar study indications, population, and design (prospective study with a long-term follow-up with more than 100 subjects), have reported the incidence of recurrence at 12 months to range from 3.5% to 5.2%. (8, 9).

95% confidence intervals obtained from incidence rates between 3.5% and 5.2% with N=100 subjects are shown below. Precision of the recurrence rates range from \pm 3.6% to \pm 4.4% as the recurrence rate increases.

	Recurrence rate at 12-month (1 year)						
	3.5%	4.0%	4.5%	5.2%			
N	100	100	100	100			
95% CI	[0.0 % - 7.1 %]	[0.2% - 6.7%]	[0.4% - 8.6%]	[0.8% - 9.6%]			
accuracy (+/-)	3.6%	3.8%	4.1%	4.4%			

Anticipating an attrition rate of 20% at 12 months, 125 subjects will be enrolled for this study.

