Indication for ventral hernia surgery		х					

Study procedures and assessment are described in the study schematic below:

Page 8 of 18

		Version	[Final v3.0]		Page 9 o	f18		Medtronic
Procedure/Assessment (D	Screening Pay-30 to 0)	Operative (Day 0)	Discharge Assessment	1 Month (±14 days) Follow-up	3 Month (±14 days) Follow-up	12 m (±30 Follo	onths days) w-up	24 months (±30 days) Follow-up
	Can be con	nbined		(Visit)	(Visit)	(Vi	sit)	(Visit)
Type of access, defect closure and Surgical technique approach		х						
Mesh size, lot number, positioning and fixation		х						
Antibiotic prophylaxis		Х						
Area of mesh overlap		Х						
Surgeon satisfaction questionnaire		х						
Adverse events assessment		Х	Х	Х	Х	>	K	Х
Length of hospital stay			Х					
Hernia recurrence/reoperation				Х	Х	>	κ	Х
Study exit								X

6. Determination of Sample Size

Sample size has been determined based on an acceptable level of accuracy for the estimated rate of hernia recurrence at 12 months (primary endpoint).

Previous studies^{1,2} of the predicate device (Proceed[™] Surgical mesh) with similar study indications, population, and design (prospective study with a long-term follow-up with more than 100 subjects), have reported the incidence of recurrence at 12 months to range from 3.5% to 5.2%.

95% confidence intervals obtained from incidence rates between 3.5% and 5.2% with N=100 subjects are shown below. Precision of the recurrence rates range from \pm 3.6% to \pm 4.4% as the recurrence rate increases.

	Recurrence rate at 12-month (1 year)								
	3.5% 4.0% 4.5% 5.2%								
N	100	100	100	100					
95% CI	[0.0 % - 7.1 %]	[0.2% - 6.7%]	[0.4% - 8.6%]	[0.8% - 9.6%]					
accuracy (+/-)	3.6%	3.8%	4.1%	4.4%					

Anticipating an attrition rate of 20% at 12 months, 125 subjects will be enrolled for this study.

PPDS Statistical Analysis Plan	
Version [Final v3.0] Page 10 of 18	Medtronic

7. Statistical Methods

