7.9. Evaluation of Objectives

Study objectives will be assessed through study endpoints measurement.

The primary endpoint is incidence of hernia recurrence within 12 months following Parietene[™] DS Composite Mesh use in ventral hernia repair.

Incidence of hernia recurrence within 12 months will be measured on the FAS subjects and using the following calculation formula:

[Subjects with Recurrence diagnosed within the first 12month following surgery]

[Subjects with Recurrence diagnosed within the first 12month following surgery + Subjects free of recurrence with a follow-up ≥12months]

A confirmatory analysis of primary endpoint will be run using Per Protocol Analysis Set.

Secondary endpoints

- Incidence of adverse device effects (ADEs) intra-operatively, at discharge, within 1 month, 3 months, 12 months, and 24 months following Parietene[™] DS Composite mesh use in ventral hernia repair will be primarily assessed based on FAS, and secondarily using PPAS and SAS.
- Incidence of hernia recurrence at 1, 3 and 24 months. The evaluation of hernia recurrence will be performed during a physical examination, using the formula described previously, according to the different time-points, and based on FAS and PPAS.
- Time to hernia recurrence and time to adverse device effect occurrence (from surgery time-point), will be assessed using Kaplan Meyer estimates. FAS and PPAS will be used for time to hernia recurrence, while FAS, PPAS and SAS will be used for time to ADE occurrence analysis. Time to Device-related AEs occurrence may also be assessed using Kaplan Meyer estimates.
- Carolinas Comfort Scale[™] QOL questionnaires completed pre-operatively and at 1, 12 and 24 months postoperatively will be analyzed using the Carolina Comfort Scale User Guide recommendations and programming code (see Appendix B), and based on FAS and on PPAS.

Several Subgroup analyses will be performed. Comparative analyses will be performed by hernia type (primary hernia versus incisional hernia) on overall subjects and on a subgroup of subjects with robotically assisted laparoscopic repair. Results of subjects operated with robotically assisted laparoscopic repair will also be compared with subjects operated with a traditional Laparoscopic procedure.

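### The primary recurrence ratio counts early leavers only if they recurred: if drop-out is unrelated to recurrence, a true 5.0% is reported as about 5.2% to 5.6%

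*SAP*

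**What the plan says.** The SAP 7.9 numerator is "Subjects with Recurrence diagnosed within the first 12month following surgery". The denominator is that group plus "Subjects free of recurrence with a follow-up ≥12months".

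Protocol 14.3.1 agrees: "Incidence of hernia recurrence within 12 months will be calculated on the FAS subjects who reach the 12-month follow-up", and it adds subjects who recurred earlier, "even if the subject has withdrawn from the study before the 12-month assessment". Neither document gives a place to a subject who leaves before month 12 without a recurrence. SAP 7.4 allows no imputation outside the quality-of-life questionnaire.

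The plan expects leavers. Protocol 14.5 says: "Anticipating an attrition rate of 20% at 12 months, 125 subjects will be enrolled for this study".

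For recurrence at 1, 3 and 24 months, SAP 7.9 reuses the ratio, "using the formula described previously, according to the different time-points". Protocol 14.3.2 says: "Incidence of hernia recurrences will be calculated on the FAS subjects who reach the corresponding time point", and that bullet does not mention subjects who recurred and then left.

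A Kaplan-Meier analysis of time to recurrence is planned on the FAS and PPAS (SAP 7.9; also Protocol 14.1 and 14.3.2), but as a secondary endpoint. It is not named as the source of the 12-month rate.

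**The concern.** A proportion among completers, or a censoring-adjusted estimate, treats leavers the same way whatever their outcome. This ratio does not: leavers with an event stay in and leavers without one are removed. The estimate is then off target even when drop-out is harmless, by an amount that depends on how many leave, when they leave and how early recurrences are found. The plan has no step that would show the reader that amount.

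This is the only primary endpoint, and it is reported as a count, a percentage and a 95% CI. The interval is centred on the shifted value and so does not correct it. The same rule at 24 months would matter more if subjects keep leaving.

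**Working it through.** **Inputs.** N = 125, 20% attrition at 12 months, and 3.5% to 5.2% recurrence at 12 months (Protocol 14.5, SAP 6). Visits at 1, 3, 12 and 24 months (Protocol 10.1). Assumed, not stated: a true risk of 5.0% (inside the documents' range), constant hazards, drop-out independent of recurrence, and an attended 12-month visit counted as 12 months of follow-up.

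**1. The plan's own figures.** 100/(1 − 0.20) = 125. The half-width 1.96·√(p(1 − p)/100) gives 3.60, 3.84, 4.06 and 4.35 points at 3.5%, 4.0%, 4.5% and 5.2%. These match the printed 3.6, 3.8, 4.1 and 4.4.

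**2. General form.** Let p be the true risk, d the attrition, and f the share of leavers' 12-month recurrences that are diagnosed before they leave. The ratio's expected value is approximately

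R = p(1 − d + df) / [p(1 − d + df) + (1 − p)(1 − d)].

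With p = 0.05 and d = 0.20:
- f = 0 gives 0.040/0.800 = 5.0% (no bias).
- f = 1 gives 0.050/0.810 = 6.2%.

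**3. Recurrences seen as they occur.** λ = −ln 0.95 = 0.0513 and μ = −ln 0.80 = 0.2231.
- Seen before leaving: λ/(λ + μ) × (1 − 0.95 × 0.80) = 0.1869 × 0.24 = 0.0449.
- Event-free and still followed: 0.95 × 0.80 = 0.760.
- R = 0.0449/0.8049 = **5.57%**, about 5.6 events over 100.6 subjects.
- Attrition of 10% to 30% gives 5.3% to 6.0%.

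**4. Recurrences found only at scheduled visits.**

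| Interval (months) | Recurrence probability | Still in study at visit | Detected |
|---|---|---|---|
| 0–1 | 0.00427 | 0.9816 | 0.0042 |
| 1–3 | 0.00848 | 0.9457 | 0.0080 |
| 3–12 | 0.03726 | 0.8000 | 0.0298 |

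The total detected is 0.0420, so R = 0.0420/(0.0420 + 0.760) = **5.24%**. Unscheduled visits (Protocol 10.5) would move this towards 5.57%.

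**5. Other true risks, 20% attrition.**

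| True | Scheduled visits only | Seen as they occur |
|---|---|---|
| 3.5% | 3.67% | 3.91% |
| 4.5% | 4.72% | 5.02% |
| 5.0% | 5.24% | 5.57% |
| 5.2% | 5.45% | 5.80% |

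**6. Drop-out related to recurrence.** Let leavers have k times the stayers' risk q, with the overall risk held at 5.0%: q = 0.05/(0.8 + 0.2k). Then R = q(0.8 + 0.2kf)/[q(0.8 + 0.2kf) + 0.8(1 − q)].
- Seen as they occur, exits spread evenly (f = 0.5): 5.59% at k = 1, 5.15% at k = 2, 4.85% at k = 3.
- Scheduled visits only (f = 0.2, since step 4 gives 0.0420 = 0.05(0.8 + 0.2f)): about 4.9% at k = 1.5 and 4.6% at k = 2.

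**7. 24 months, same hazards continuing.** The true risk is 1 − 0.95² = 9.75%. Cumulative attrition is 1 − 0.80² = 36%. Event-free and followed is 0.9025 × 0.64 = 0.5776.
- Seen as they occur: 0.1869 × (1 − 0.5776) = 0.0789, so R = 0.0789/0.6565 = **12.0%**.
- Scheduled visits only: 0.0420 + 0.0475 × 0.64 = 0.0724, so R = 0.0724/0.6500 = **11.1%**.

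**8. The alternative.** A visit-interval life table divides the recurrences found at each visit by the previously event-free subjects assessed there. From the step 4 inputs the three ratios are 0.00427, 0.00851 and 0.03774, and 1 − 0.99573 × 0.99149 × 0.96226 = 5.0%. In simulation (N = 125, exact event times) Kaplan-Meier averaged 5.00% at 12 months and 9.73% at 24.

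**The case against.** The strongest reply is that the effect is small, its direction is not assured, and most of the remedy is already planned. Much of this stands.

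- **Direction.** A reader might infer that the rate is biased upward without qualification. That holds only if drop-out is unrelated to recurrence, which the documents do not say. Step 6 shows the bias vanishing or reversing with modestly higher risk in leavers. Kaplan-Meier and life tables rest on the same independence assumption, so they do not cure that case.
- **Size.** Quoting 5.6% alone would give the top of the range, because recurrence is mainly looked for at scheduled visits.
- **Consequence.** A reader might infer that the device would be judged worse than the predicate. The analysis is descriptive (Protocol 14.1, SAP 7.2 and 7.5). There is no success threshold and no test against 3.5% to 5.2%, a range used only to size the study.
- **Precision.** A reader might infer that the ratio wastes much information. With visit-only detection, the simulated SD is 2.22 points for the ratio and 2.13 for the life table, a negligible gain. The wider gap with exact event times (2.29 against 2.06) does not match how recurrence is mostly found here.
- **24 months.** No 24-month attrition is stated. A reader might also infer that the documents prescribe two different 24-month rates. Protocol 14.3.2 is silent on early recurrers in its recurrence bullet, while the adjacent adverse-device-effect bullet includes subjects with recurrence. This is a wording mismatch to reconcile.

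What does not fall is the rule itself. It selects on the outcome and misses its target even under harmless drop-out. The planned Kaplan-Meier analysis is not tied to the 12-month estimate, and no count of the event-free leavers excluded is specified.

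**Conclusion.** The concern holds in a limited form. SAP 7.9 and Protocol 14.3.1 set an explicit, outcome-dependent inclusion rule for the primary rate. Under independent drop-out, constant hazards and 20% attrition, a true 5.0% is reported as about 5.2% to 5.6%, a shift of 0.2 to 0.6 points. This is small against a half-width of 3.6 to 4.4 points, and it runs against the device. At 24 months, if attrition continues at the same rate, 9.75% becomes about 11.1% to 12.0%.

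The change is worth making because the error varies with attrition and detection timing that the reader cannot see, and the remedy is cheap. It does not invalidate the study.

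**What to change.** In SAP 7.9 and Protocol 14.3.1, name as the primary estimate the 12-month cumulative incidence of recurrence on the FAS with its 95% CI. Take it from a visit-interval life table or from the Kaplan-Meier analysis already planned. Censor event-free leavers at their last documented recurrence assessment. The exit date will not do: Protocol 10.12.5 defers loss to follow-up to the end of the study, and running event-free time to that date would count every unrecorded recurrence as a success (0.0449 of 1, or about 4.5% for a true 5.0%).

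At minimum, print this estimate and its CI beside the ratio, with the number of event-free leavers the ratio excludes. State that the estimate assumes drop-out independent of recurrence. Use the same estimator at 24 months, and align the 24-month denominator wording of SAP 7.9 and Protocol 14.3.2.

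The cost is a few sentences in each document and no new data. The one drawback is that the primary figure is no longer a plain proportion, so keep the ratio as a supportive result for comparison with published rates.

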7.12. Changes to Planned Analysis

Some minor changes were made in this SAP in regard to the statistical methodology as described in CIP v1.0 document. These changes are related to Analysis Sets definitions and the use of these analysis sets for endpoints assessment.

From CIP v1.0, analysis sets were defined as follows:

- the Full Analysis Set (FAS, including any subject enrolled and receiving study device) representing the primary analysis population,
- the Per Protocol Analysis Set [PPAS, a subset of the FAS of subjects who meet the primary endpoint (12month assessment) and who did not deviate (major) from the protocol], as confirmatory analysis and,
- the Safety Analysis Set (any subject with skin incision including those who are 'screen failure during surgery') for safety and efficacy analysis

From SAP v1.0, analysis sets are defined as follows:

- Full Analysis Set (FAS): including any subject enrolled and receiving study device, representing the primary analysis population, for Efficacy and Safety analyses.
- Per Protocol Analysis Set (PPAS): a subset of the FAS of subjects who meet the primary endpoint (12month assessment) and who did not deviate (major) from the protocol, as confirmatory analysis for Efficacy and Safety analyses,
- Safety Analysis Set (SAS): any subject pre-operatively eligible with skin incision including those who are 'screen failure during surgery', used for Safety analysis.

Any major change in planned analysis as described in this SAP would result in SAP amendment.

Validation level I will be applied for endpoints evaluated at the first interim analysis.

First interim analysis (Safety analysis at 3-months) will evaluate subject's disposition, screening data, demographics characteristics and occurrence of procedure or device-related AE occurring within 3-month from surgery (see IA#1 parameters in section 7.8.1.).

Validation level III will be applied for any endpoint evaluated during second interim analysis or final analysis.

Validation levels are defined as follows:

- Level I: The peer reviewer independently programs output and then compares the output with that generated by the original Statistical Programmer.
- Level II: The peer reviewer reviews the code; where appropriate, performs manual calculations or simple programming checks to verify the output.
- Level III: Original Statistical Programmer performs a visual inspection of the code and output to confirm functionality.

9. References

10. Statistical Appendices

- A. Quality of Life (QOL) Carolina Comfort Scale (CCS) Questionnaire
- B. CCS QOL Questionnaire User Guide
